10.1 SAMPLE SIZE

Based on the information available, around 15% of the patients to whom a TAVI has been implanted show signs of amyloidosis. Mortality at two years after a TAVI is about 17% and in patients with amyloidosis, it is estimated to be 40%. Based on this data, for a significance level of 5% (error $\alpha = 0,05$) and a power of 80% (error $\beta = 0,20$), a sample size of 306 patients is estimated, assuming 5% of follow-up losses, it was decided to include 321 patients. The results in which the calculations are based are given at 2 years, if not significant; monitoring would continue up to 3 years.

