 1. DATA COLLECTION
 2. DATA MANAGEMENT
 3. DATA CONFIDENTIALITY
14. PRACTICAL USE OF THE RESULTS
15. ETHICS
16. ANNEX
 1. ECHOCARDIOGRAPHY PROTOCOL
 2. SCINTIGRAPHY PROTOCOL
 3. DECLARATION OF HELSINKI

1. STUDY SUMMARY

Study title and code	Prognostic impact of cardiac amyloidosis in patients with severe aortic stenosis who underwent percutaneous implantation of an aortic prosthesis (AMY-TAVI)
Study type and design	Observational analytical of multicenter prospective cohorts.
Number and characteristics of patients	321 patients to whom a TAVI has been implanted by severe degenerative AoS.
Study duration	Recruitment period: All the consecutive patients to whom a non-invasive diagnostic study of amyloidosis (scintigraphy with tecnecio ⁹⁹ pyrophosphate and electrophoresis of proteins in the blood) and to whom a percutaneous aortic prosthesis for severe aortic stenosis has been implanted. Follow-up period: clinical and echocardiographic monitoring will be done before discharge, in consultation at three, six, twelve, and twenty-four months. Inclusion: 1 year Follow-up: 2 years Data analysis: 6 months Total: 3 years and 6 months
Events	Main event: cardiovascular events (cardiovascular death, stroke, heart attack), death from any cause, readmission for cardiac insufficiency, pacemaker implantation, functional assessment
Participating countries and centers	Various Spanish and international centers will be invited to participate.

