8. OBJECTIVES

8.1 PRIMARY OBJECTIVE

A multicentre prospective study of cohorts consisting of two cohorts from patients who have been implanted with percutaneous aortic prosthesis as treatment for the severe degenerative aortic stenosis and compare the overall mortality and that for

cardiovascular and admissions for heart failure in the 2-year follow-up of patients diagnosed with amyloidosis (by GT99 and EFP) versus those that do not have it.

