9. DESIGN

A multicentre, analytical, observational study of two cohorts. One cohort will be constituted by the patients to whom a TAVI will be implanted, and that meet non-invasive diagnostic criteria of TTR amyloidosis (capturing of radiotracer in grades 2 and 3 and absence of monoclonal gammopathy the PE of urine or serum). The other cohort will be constituted by patients whose TAVI implants do not meet the diagnostic criteria for TTR amyloidosis.

A clinical and echocardiographic follow-up will be done in all patients for two years.

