10. STATISTICAL ANALYSIS PLAN AND SAMPLE SIZE

10.1 STATISTICAL ANALYSIS

A descriptive analysis of both cohorts defining their clinical and angiographic profiles and a comparative study of the two groups (cohorts) will be performed. The categorical variables are expressed in percentages and the continuous as medium value \pm standard deviation. The relative risk and the “Hazard Ratio” will be used as measures of effect when variables are analyzed with a temporal component, always with a confidence interval of 95%. For the comparison of categorical variables, the Chi-square or the Fisher test will be used. To compare continuous variables, the “t” of student test or analysis of variance will be used. The variables of time to event, such as the analysis of event-free survival will be analyzed by using the Kaplan- Meier technique and will be supplemented by the log-rank test. The multivariate analysis of the adverse events predictors during the follow-up will be done by means of the Cox regression model, determining the Odds Ratio for each variable.

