11.2. CLINICAL AND IMAGE FOLLOW-UP

This will be done before discharge, in consultation at three, six, and 12 months and annually thereafter. All the visits have a window period to be carried out with additional tests within this protocol, one week before and one week after the due date.

First visit (Basal Visit).

- Assessment of patient history.
- Detailed physical assessment of the patient.
- Electrocardiogram.
- Analysis.
- Echocardiographic basal study, with ventricular *strain* measurements.
- Perform 6-minute test.

Follow-up visit at 3 months (more/less one week)

- Clinical assessment.
- Analysis.
- Events assessment.

Follow-up visit at 6 months (more/less one week)

- Clinical assessment.
- Analysis.
- Perform 6-minute test.
- Events assessment.

Follow-up visit at 12 months (more/less one week)

- Clinical assessment.
- Electrocardiogram.

Prognostic impact of cardiac amyloidosis in patients with severe aortic stenosis who underwent percutaneous implantation of an aortic prosthesis

- Analysis.
- Echocardiographic study with ventricular *strain* measurements.
- Events assessment.

Follow-up visit at 24 months (more/less one week)

- Clinical assessment.
- Analysis.
- Echocardiographic study.
- Events assessment.

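### Follow-up goes to 3 years only if the 2-year result is not significant; a repeat test at an unadjusted 5% would raise the false-positive rate to about 7-8%

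*Combined protocol and SAP*

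**What the plan says.** Section 10.1 Sample Size assumes that 15% of TAVI patients have amyloidosis and that 2-year mortality is 17% after TAVI and 40% with amyloidosis. With 5% significance and 80% power it arrives at 306 patients, raised to 321 for losses. It adds that results are "given at 2 years, if not significant; monitoring would continue up to 3 years".

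Section 10.1 Statistical Analysis lists chi-square or Fisher tests, Cox regression, 95% confidence intervals and Kaplan-Meier curves, which "will be supplemented by the log-rank test". It contains no division of the 5%, no spending rule, and nothing on how a 3-year result would be tested or labelled.

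Elsewhere the horizon is 2 years:
- Section 8.1 Primary Objective compares mortality and "cardiovascular and admissions for heart failure in the 2-year follow-up of patients diagnosed with amyloidosis" with that of patients without it.
- Section 9 Design: "A clinical and echocardiographic follow-up will be done in all patients for two years".
- Section 1 Study Summary: "Inclusion: 1 year Follow-up: 2 years Data analysis: 6 months Total: 3 years and 6 months".
- The section 12 Work Plan table ends at 2 years.

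Only section 11.2, with visits "in consultation at three, six, and 12 months and annually thereafter", leaves room for a third year, and its own visit list stops at 24 months.

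**The concern.** Whether follow-up continues depends on the test result. A significant 2-year result ends the matter, and a non-significant one buys another year of deaths. If the comparison is then repeated at the same 5% level, a false-positive result can arise at either test, so the chance of at least one exceeds 5%. Announcing the second look in advance does not control this unless its significance level is also set in advance.

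The rule also lets the 2-year p-value choose the horizon of the main result. A 3-year hazard ratio reported because the 2-year test failed does not answer the 2-year question in the primary objective. The section on practical use says the results will inform screening and early treatment, so the error rate behind a significant result matters.

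**Working it through.** **Inputs from section 10.1 Sample Size.** Amyloidosis 15%; 2-year mortality 40% and 17%; significance 5%; power 80%; 306 patients before losses. Sidedness is not stated; two-sided is taken here and one-sided is shown as well.

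**1. The plan's own figure.** The document does not name its formula. The log-rank events formula comes close:
- Hazard ratio = ln 0.60 / ln 0.83 = 2.74.
- Events = (1.960 + 0.842)² / [0.15 × 0.85 × (ln 2.74)²] = 60.5, rounded up to 61.
- Proportion dying by 2 years = 0.15 × 0.40 + 0.85 × 0.17 = 0.2045.
- N = 61 / 0.2045 = 299, against the stated 306.
- At 306 patients there are 306 × 0.2045 = 62.6 deaths and power is 81.3%, against the stated 80%.
- 306 × 1.05 = 321.3, matching 321.

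The pooled two-proportion formula gives 211 (244 with continuity correction) and does not reproduce 306.

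**2. Information at the first look.** The documents give no 3-year mortality, so constant hazards are assumed:
- Dead by 3 years = 0.15 × (1 − 0.60^1.5) + 0.85 × (1 − 0.83^1.5) = 0.0803 + 0.2073 = 0.2875.
- Information fraction f = 0.2045 / 0.2875 = 0.711.

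**3. Overall false-positive rate.** Under no effect the two test statistics are approximately bivariate normal with correlation √f. The rate is P(|Z₁| > 1.96 or |Z₂| > 1.96).

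| f | Two-sided 5% at both looks |
|---|---|
| 0.9 | 6.5% |
| 0.8 | 7.1% |
| **0.711** | **7.5%** |
| 0.6 | 8.0% |
| 0.5 | 8.3% |

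If the 5% is one-sided, the rate is 7.3% at f = 0.711 and 6.3-8.0% for f = 0.9-0.5. The independent-tests figure of 9.75% does not apply, because the 3-year data contain the 2-year data.

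**4. Simulation check.** In 40,000 null studies (306 patients, 46 with amyloidosis), the rate rose from 4.9% at 2 years to 7.4% with the extension for the log-rank test. For the chi-square test on deaths it rose from 5.0% to 7.8%. With no true effect, the extension is triggered about 95% of the time (1 − 0.05).

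**5. Levels that would restore 5% at f = 0.711.** Either 0.0327 at both looks, or 0.017 at 2 years and 0.044 at 3 years (O'Brien-Fleming type). In the null simulation, log-rank tests at 0.033/0.033 and 0.017/0.044 both gave 4.9%.

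**6. Effect of those levels on 2-year power.**

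| 2-year level | Events formula | Simulated log-rank (20,000 runs) |
|---|---|---|
| 0.05 | 81% | 93% |
| 0.033 | 76% | 90% |
| 0.017 | 68% | 86% |

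All these figures concern one outcome, mortality. Multiplicity across the several outcomes in the summary and primary objective is a separate matter and is not counted.

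**The case against.** The strongest objection is that the repeat test is inferred. The plan says only that monitoring would continue; a later descriptive Kaplan-Meier curve or hazard ratio would also fit the words, and then no error rate is inflated. This stands as a limit on the claim: 7-8% is conditional on an unadjusted repeat. It does not remove the point. The extension is tied to significance, nothing gives the third year a non-confirmatory role, and the tests listed would naturally be applied again.

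Second, the planned horizon is legible: several sections say 2 years, and the trigger is disclosed. That is fair. The difficulty is that the trigger can override that horizon.

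Third, the size depends on calendar timing. With uniform accrual over one year, suppose the first log-rank test runs when the last patient reaches 2 years and uses all available follow-up. If the second look is capped at 3 years per patient, f is about 0.86 and the rate about 6.8%. If both looks use all follow-up, f is about 0.76 and the rate about 7.3%. Both lie within the 6.5-8.3% range, and neither returns to 5%.

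Fourth, this is an observational cohort reporting estimates with intervals, and the inflation is modest. That argues against treating the defect as fatal. The plan nevertheless states a 5% level and a power, and an overall rate of 7.5% is half as large again as the stated level.

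**Conclusion.** The concern holds, as something that should be fixed. The plan contains a significance-triggered extension with no control of the error rate and no defined role for the third year, and the rule conflicts with the 2-year horizon stated elsewhere. If the mortality comparison is repeated at 5%, the false-positive rate is about 7.5% with the log-rank test and 7.8% with the chi-square test. The range is 6.5-8.3% for information fractions of 0.9 to 0.5. This rests on two assumptions: that the 3-year comparison would be an unadjusted test at 5%, and that hazards are constant. The second affects only the size within that range. The gap in the plan and the result-dependent horizon do not depend on either.

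**What to change.** **Preferred.** In section 10.1 Sample Size, state that the single confirmatory test is overall mortality at 2 years at two-sided 5%, the outcome behind the sample size. Delete the condition on non-significance. Say that any 3-year result is descriptive, a hazard ratio with 95% confidence interval, whatever the 2-year p-value. This is wording only and keeps the planned 2-year power. All that is lost is a second, unadjusted chance at significance.

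**Only if a confirmatory 3-year test is wanted.** Fix both levels before any 2-year data are seen, for example about 0.033 at each look, or 0.017 at 2 years and 0.044 at 3 years, and state the information fraction assumed (0.711 here). The cost is 2-year power: from 81% to 76% or 68% by the events formula that comes close to the plan's 80%, or from 93% to 90% or 86% by direct simulation. The simulated figures suggest that the formula understates power with a 15:85 split, so the loss may be nearer the smaller figures. The 3-year look would recover power overall.

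**Either way.** Reconcile any third year with sections 1, 8.1, 9, 11.2 and 12. Following all patients for a third year would be a real added cost beyond the present timetable, and the preferred change does not require it.

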11. PATIENTS FOLLOW-UPS

11.1 INITIAL PATIENT ASSESSMENT

An initial inclusion visit will assess whether the patient is a candidate who meets the inclusion criteria and none of the exclusion ones. After being informed, if they accept, the informed consent must be signed. The following data must be recorded:

- **Clinical parameters:** age, sex, height, weight, body mass index, body surface, cardiovascular risk factors, medication intake, background interests, history of heart disease, presence of ischemic heart disease, cerebrovascular accident, peripheral artery disease, chronic obstructive pulmonary disease, symptoms (angina, syncope, dyspnea according to grades of the NYHA, other symptoms), blood pressure, heart rate, evidence of heart failure, assessment of functional class by means of 6MT and fragility assessment.
- **Analytical parameters:** hematocrit, NT-proBNP, Troponin I, electrolytes, C-reactive protein, creatinine, glomerular filtrate.
- **Protein electrophoresis:** Rating presence of the monoclonal component
- **Scintigraphy with TC⁹⁹:** Assessment of values of tracer uptake.
- **Device parameters:** Type of prosthesis, dimensions, expandable/ self-expanding ball, post-dilatation.
- **ECG parameters:** Rhythm, PR duration, pacemakers, implantable cardioverter defibrillator, QRS duration.

- The 6 minute-test: All patients in the study will have a test of 6 minutes before implantation and 6 months follow-up, according to the protocol after a TAVI, in order to carry out an objective functional assessment of the functional capacity. The distance covered will be determined, the variation of oxygen saturation by means of non-invasive pulse oximetry before and after the test and the appearance of symptoms with the effort according to the Borg scale.

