8.1 SECONDARY OBJECTIVES

1. As part of the hypothesis, we will analyze separately the impact of the presence of amyloidosis on the requirements of permanent pacing (permanent pacemaker implantation, pacemaker dependence, changes in the conduction system)
2. Determine the impact on the functional class (measured by using the 6-minute test) of the coexistence of TTR amyloidosis in patients with a TAVI implant.
3. Validate echocardiographic patterns of cardiac amyloidosis diagnosed by ventricular strain in a population with EAS undergoing a TAVI implant, as well as study the evolution of these patterns mid-term.

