13. DATA MANAGEMENT

13.1. DATA COLLECTION:

All the patients will receive standard treatment according to clinical practice guidelines and consensus in force. The criteria for inclusion/ exclusion will be assessed in all of them to confirm the feasibility of entering the study, which will be offered, explained, and then the appropriate informed consent collected. Subsequently, following the predefined protocol, a number of epidemiological variables, clinical, laboratory, electrocardiographic, echocardiographic, functionals, scintigraphy with Tc⁹⁹basals of the patient will be collected before discharge. All previously detailed. All the data will be collected in the Data Collection Logbook (DCL), which is designed to register all the data required in the protocol and collected by the researcher. The data on the DCL will be coded. The data entry will be done by the researcher or the person assigned by them, and then that data will be transferred to the database of the study. The researcher or the appointed person in their team commits to completing the DCL on each visit made by the participant. All data corrections in the DCL will be made by the researcher or the person assigned in their team in accordance with the instructions given. After the last visit from the participant and the closure of the DCL, the researcher must attest, by signing the DCL, the authenticity of the data collected in the DCL, the coherence between the data in the DCL and the data contained in the source document.

13.2 DATA CONFIDENTIALITY:

All documents and information provided to the researchers by the promoter regarding the study are confidential. Both the researcher and their collaborators undertake to use the information provided only within the framework of this study to carry out this protocol. This commitment remains as long as the confidential information has not been made public by the promoter. The protocol delivered to the researcher can be used by them or their collaborators to obtain informed consent from the participants entering the study. It should not be disclosed to third parties without the written consent of the promoter. This information will be treated in accordance with the rules of professional secrecy. The screening list must be completed when the researcher verifies that the participant can enter the study after confirming their record and medical history.

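### The 6-minute walk is measured before implantation and at 6 months, but the analysis plan gives the baseline walk no role in answering secondary objective 2

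*Combined protocol and SAP*

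**What the plan says.** Secondary objective 2 (section 8.1) reads: "Determine the impact on the functional class (measured by using the 6-minute test) of the coexistence of TTR amyloidosis in patients with a TAVI implant". It names no time point and no summary measure.

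Section 11.1 schedules the walk twice: "All patients in the study will have a test of 6 minutes before implantation and 6 months follow-up". The main measurement is distance: "The distance covered will be determined". The visit list in 11.2 and the table in section 12 agree with these two occasions.

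On method, section 10.1 says: "To compare continuous variables, the “t” of student test or analysis of variance will be used". The only multivariable model is for events: "The multivariate analysis of the adverse events predictors during the follow-up will be done by means of the Cox regression model". That model does not apply to a walking distance. The effect measures for which 10.1 promises 95% confidence intervals are the relative risk and the hazard ratio, so no interval is promised for a difference in metres.

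On timing, section 13.1 describes the baseline data differently from 11.1: "functionals, scintigraphy with Tc⁹⁹basals of the patient will be collected before discharge". A walk done before discharge need not precede implantation.

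**The concern.** Cohort membership depends on whether the patient has TTR amyloidosis, not on randomisation. Section 4 describes the disease as presenting with heart failure, orthostatic hypotension and syncope, and as linked to low-flow, low-gradient stenosis. A lower walking distance before the valve is placed is therefore plausible in the amyloidosis cohort.

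Two things are at stake. If the 6-month distance alone is compared, a cohort that started lower and gained as much as the other could be reported as having done worse after TAVI. In addition, leaving the baseline walk out of the model leaves explainable between-patient variation in the error term, so the confidence interval is wider than it need be. Both would apply even if every patient completed both tests; who is missing at 6 months is a separate question.

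**Working it through.** The plan states no sample size or power for the walk (306 and 321 patients refer to mortality), so there is no figure of its own to reproduce.

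**Inputs from the protocol.** 321 patients; about 15% with amyloidosis, so 48 v 273. Two-year mortality is 40% with amyloidosis and 17% after TAVI, the latter applied here to the cohort without amyloidosis.

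**Assumptions (not in the documents).** Constant hazard; all survivors tested at 6 months; SD 110 m at both times (range 90-130 m); baseline gap 40 m (range 20-60 m); baseline-to-6-month correlation r = 0.5-0.7; two-sided 5% level.

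**Patients alive at 6 months**
- Amyloidosis: 48 × 0.60^(6/24) = 42.2 (mortality 12.0%).
- No amyloidosis: 273 × 0.83^(6/24) = 260.6 (mortality 4.6%).

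**6-month distance alone**
- SE = 110 × √(1/42.2 + 1/260.6) = 110 × 0.1659 = 18.25 m.
- With a 40 m gap and equal gains, the 6-month difference is still 40 m. z = 40/18.25 = 2.19, and the probability of significance is Φ(2.19 − 1.96) + Φ(−2.19 − 1.96) = 59%.
- With the 40 m gap, SD 90 m gives 76% and SD 130 m gives 46%. With SD 110 m, a 20 m gap gives 20% (19.5% before rounding) and a 60 m gap gives 91%.

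**Precision with baseline adjustment.** Adjusted SE = SE × √(1 − r²), ignoring the small loss from correlation between cohort and baseline. The detectable difference is (1.96 + 0.84) × SE.

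| Analysis | Share of variance removed | 95% CI half-width | Detectable at 80% power |
|---|---|---|---|
| 6-month value alone | none | 36 m | 51 m |
| Adjusted, r = 0.5 | 25% | 31 m | 44 m |
| Adjusted, r = 0.7 | 49% | 26 m | 37 m |

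**What adjustment does to the gap.** With equal SDs the slope equals r, so the adjusted model leaves (1 − r) of a stable baseline gap. With a 40 m gap and equal gains:

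| r | Gap left | Adjusted SE | Probability of significance |
|---|---|---|---|
| 0.5 | 20 m | 15.8 m | 24% |
| 0.6 | 16 m | 14.6 m | 19% |
| 0.7 | 12 m | 13.0 m | 15% |

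This is well below 59% but above 5%.

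**Change score.** In this scenario the difference in mean change is zero, so no gap is left. Its SE is 18.25 × √(2(1 − r)): 18.25 m at r = 0.5 (no gain over the 6-month value) and 14.1 m at r = 0.7. Below r = 0.5 it is less precise than the 6-month value alone; at r = 0.3 the half-width is 42 m against 36 m.

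Neither analysis is best on both counts, which is why the target has to be stated.

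**The case against.** The strongest objection is that a reader might infer from 10.1 that the baseline walk will be ignored and the raw 6-month distance tested. The documents do not say so. A t test on the change from baseline fits the same sentence, and the walk is among the baseline clinical parameters in 11.1, so the planned comparison of the cohorts' clinical profiles may well show the baseline difference. This stands: the defect is an unspecified analysis, not a declared wrong one. It still needs correcting, because an open choice between 6-month value and change can be made after the data are seen, and the choice affects both the answer and its precision.

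A second tempting inference is that a persisting deficit would be a false finding. Objective 2 asks about the impact of coexisting amyloidosis in patients with a TAVI implant. Amyloidosis would normally precede the baseline walk, so a lower start can be part of that impact, and the total difference at 6 months is a legitimate, if confounded, target. The 59% is an error rate only when the target is differential change. This also stands.

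Third, baseline adjustment alone is not a cure in non-randomised cohorts, as the 15-24% above shows. That is a reason to report the change beside it, not to leave baseline out. Finally, the SD, gap and correlation are assumptions, and without a baseline gap there is no mixing. The loss of precision remains at any r above zero.

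**Conclusion.** The point holds in a limited form. The protocol collects a baseline walk, names only an unadjusted comparison for continuous variables, and does not say how the baseline walk enters the answer to objective 2.

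If the 6-month distance alone is compared and read as change after TAVI, a stable 40 m deficit would be significant in about 59% of studies at SD 110 m. If baseline is left out of the model, 25-49% of the unadjusted variance is retained unnecessarily at r = 0.5-0.7. Both sizes rest on the assumed SD, gap and correlation and on the plan's mortality rates under constant hazard. This is a secondary objective without stated power, so the matter does not touch the mortality comparison or its sample size.

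**What to change.** In section 10.1:

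1. State the target for objective 2: the total difference at 6 months, or the differential change after TAVI.
2. Analyse 6-month distance with a linear model on cohort and pre-implantation distance, and report the adjusted difference with a 95% CI.
3. Report with equal prominence the baseline difference and the between-cohort difference in mean change, with 95% CI for the latter.
4. For missing baseline walks, use multiple imputation with cohort in the imputation model, or complete cases. Do not impute the overall mean: where the cohorts are expected to differ at baseline, it hides the gap being adjusted for.

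Reconcile section 11.1 (walk before implantation) with 13.1 (baseline functional data before discharge), so that the covariate is a true pre-implantation value.

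The cost is a few sentences. No new measurements are needed, provided the baseline walk is done before implantation. The small downside is that the adjusted and change analyses may differ and must then be interpreted together, in the light of the stated target.
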